(3). The collective process yielded a novel wheelchair exercise training program that is ready to be examined for feasibility before testing within a formal clinical trial.

- Ultimately, this study extends [name] line of research and may initiate a significant paradigm shift in rehabilitation research and practice by providing a critically needed home-based exercise training program for enhancing health, quality of life, participation, and independence of wheelchair user with MS.

Objectives

- To examine the feasibility, acceptability, and initial efficacy of a stakeholder-informed, home-based, remotely supported and supervised exercise training program for wheelchair users with multiple sclerosis (MS) compared to an attention/contact wellness control program.
- Feasibility will be operationalized using ongoing assessment of recruitment, retention, and safety. We hypothesize that the intervention will be feasible in terms of reaching recruitment goals (n=24; 12 per group) within a one-year period, retaining ≥80% of those participants through the full 16-week study period, and safe in terms of <10% of participants reporting adverse events. We are defining our recruitment goals as participants who matriculate and are randomized, therefore we aim to consent up to 28 participants.

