- Acceptability will be operationalized as participant satisfaction and perceptions measured in post-intervention formative surveys and interviews. We hypothesize that a greater proportion of participants in the SPIN exercise training condition will report high satisfaction and positive perceptions regarding the exercise training program compared with the attention/contact wellness control condition.
- The study will further examine changes in scientific outcomes of interest (i.e., metabolic health, MS symptoms, and exercise behavior change) for determining effect size and sample size estimates in powering a larger clinical trial. We hypothesize that the SPIN exercise training intervention program will lead to greater improvements in metabolic health outcomes (i.e., HbA1c, cholesterol, glucose, and triglycerides), MS symptoms (i.e., fatigue, pain, depression, and quality of life) and exercise behavior compared to the attention/control wellness program.

Study Design

- Parallel group, randomized controlled trial

- The study is funded for a 2 year period and participants will be involved in study procedures for approximately 6 months.
- The primary outcome of interest is feasibility (i.e., recruitment, retention, and safety). The secondary outcome of interest is acceptability (i.e., participant satisfaction and perceptions).
- The tertiary outcomes of interest are scientific outcomes of initial efficacy(i.e., metabolic health, MS symptoms, and exercise behavior).
- Safety will be assessed in terms of incidence of participants reporting adverse events.

Study Population

- Eligibility criteria: (a) diagnosis of MS; (b) self-reported use of a wheelchair (i.e., manual wheelchair, power wheelchair, or scooter) ≥50% of the time; (c) age of 18 years or older; (d) relapse free for the past 30 days; and (e) being non-active defined as not engaging in regular physical activity (30 minutes accumulated per day) on more than 2 days of the week during the previous 6 months (i.e., not meeting current physical activity guidelines for MS). During telephone screening participants will complete an exercise pre-participation health screen and if participants report any symptoms or conditions contradictory of exercise then physician clearance will be required before enrollment.

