- All testing will be performed by trained personnel and all equipment will be calibrated daily before testing. If an individual indicates discomfort or the desire to discontinue testing, tests will be terminated immediately. All adverse events will be reported to the UTHealth Houston IRB and reviewed by the investigative team. Should any of these individuals and/or the IRB identify that any adverse event may be related to the study protocol, testing will be suspended and the protocol will be amended accordingly. Adverse events will be tracked using a REDCap database for assessing the primary study outcomes.

Statistics

- The planned enrolled sample size of 28 participants (i.e., 12 per group that matriculate and are randomized) is justified for pilot clinical trials when there is no prior information for sample size estimation.
- [name] (PI) will lead the data analyses given her expertise in both quantitative and qualitative data analyses. Participant characteristics will be reported using means/medians and standard deviations/interquartile ranges for continuous variables. Categorical measures will be presented as counts and percentages. The analysis will use the intent-to-treat principle where patients will be

analyzed in their randomization assignment. Descriptive statistics including frequencies and percentages will be utilized to assess the feasibility metrics for the primary and secondary outcomes (*Hypothesis 1 & Hypothesis 2*). The scientific outcomes in *Hypothesis 3* (i.e., metabolic health outcomes, MS symptoms, and exercise behavior) will be examined using 2 time by 2 group mixed factor ANOVA with estimation of Cohen's d values for effect sizes. Participant's change in scientific outcomes will be further examined and compared with the ≥ 0.5 SD will be considered meaningful change based on benchmarks established in previous research.

Ethics

- First, following screening all participants deemed eligible for the study will then be sent a consent form to review and sign using through REDCap. The PI will review the consent document to ensure participants understand study procedures and sign the document prior to enrollment. During consent process the research team will emphasize the voluntary nature of all research procedures and assess consent at each following contact as consent is an ongoing process.

Data handling and record keeping

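### The primary retention and safety conclusions would be drawn from percentages in about 24 people, with no confidence interval and no stated precision

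*Combined protocol and SAP*

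**What the plan says.** Study Design names feasibility, made up of recruitment, retention and safety, as the primary outcome. Objectives states it as a hypothesis with fixed cut-offs. The recruitment target is 24 randomized participants, 12 in each group, inside one year. The retention criterion is worded as "retaining ≥80% of those participants through the full 16-week study period". For safety, the program is to be judged by a separate criterion: "safe in terms of <10% of participants reporting adverse events". The same section explains that the recruitment goal counts randomized participants and that up to 28 will be consented to reach it.

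Statistics gives the analysis of the primary and secondary outcomes in one sentence: "Descriptive statistics including frequencies and percentages will be utilized to assess the feasibility metrics for the primary and secondary outcomes". The only other summary measures planned there are standard deviations or interquartile ranges for continuous participant characteristics, and Cohen's d with a half-SD criterion for the tertiary outcomes. Neither applies to the retention or adverse-event proportions. The sample size, according to the same section, "is justified for pilot clinical trials when there is no prior information for sample size estimation". It gives no precision target.

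**The concern.** The hypothesis is a statement about the program: that it is feasible, and that it is safe in the sense of a low adverse-event proportion. The planned evidence is an observed percentage set against a cut-off. With about 24 people, a percentage on the favourable side of a cut-off can sit well inside sampling error of values on the other side. A plan that reports the percentage alone does not show this.

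At stake is what the primary outcomes manuscript can properly say. Under Publication Plan, the results also go into later grant proposals. A result of 2 events in 24, reported as 8.3% and therefore safe, would be passed on without the information that the same data are compatible with a rate of 27%. The sample-size sentence gives no warning either, because it does not say what 24 participants can show about the primary proportions.

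**Working it through.** **The plan's own figure.** 2 × 12 = 24 randomized. Consenting 28 allows 28 − 24 = 4 losses before randomization (4/28 = 14.3%). The 24 has no alpha, power, effect or precision behind it, so there is no formula to reproduce.

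**Inputs.** From Objectives: n = 24 randomized, 12 per group; retention at least 80%; adverse events in fewer than 10% of participants. Assumed: a 95% confidence level.

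**Cut-offs as counts.**
- Retention, n = 24: 0.80 × 24 = 19.2, so at least 20 (19/24 = 79.2% misses; 20/24 = 83.3% meets).
- Adverse events, n = 24: 0.10 × 24 = 2.4, so at most 2 (2/24 = 8.3% meets; 3/24 = 12.5% misses).
- One arm, n = 12: 0.80 × 12 = 9.6, so at least 10; 0.10 × 12 = 1.2, so at most 1.

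**Formula.** Exact (Clopper-Pearson) limits for x of n: the lower limit is the 2.5% quantile of Beta(x, n − x + 1), and the upper limit is the 97.5% quantile of Beta(x + 1, n − x). With x = 0 the upper limit reduces to 1 − 0.025^(1/n), or 1 − 0.05^(1/n) one-sided. With x = n the lower limit is 0.025^(1/n).

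| Result | Observed | Exact two-sided 95% CI |
|---|---|---|
| Retained 20/24 | 83.3% | 62.6% to 95.3% |
| Retained 21/24 | 87.5% | 67.6% to 97.3% |
| Retained 22/24 | 91.7% | 73.0% to 99.0% |
| Retained 23/24 | 95.8% | 78.9% to 99.9% |
| Retained 24/24 | 100% | 85.8% to 100% |
| Adverse event 0/24 | 0% | 0% to 14.2% |
| Adverse event 1/24 | 4.2% | 0.1% to 21.1% |
| Adverse event 2/24 | 8.3% | 1.0% to 27.0% |
| Retained 10/12 | 83.3% | 51.6% to 97.9% |
| Adverse event 0/12 | 0% | 0% to 26.5% |
| Adverse event 1/12 | 8.3% | 0.2% to 38.5% |

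**Zero events.** Two-sided: 1 − 0.025^(1/24) = 14.2%. One-sided: 1 − 0.05^(1/24) = 11.7%. The Wilson upper limit is 13.8%. All exceed 10%, and any further event raises the limit. As a direct check, a true rate of exactly 10% gives no events in 24 with probability 0.9^24 = 8.0%.

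**Sensitivity.**
- Denominator: with all 28 consented, 0/28 gives 12.3% two-sided and 10.1% one-sided, still above 10%.
- Confidence level, safety: one-sided 90% gives 1 − 0.10^(1/24) = 9.1%, which is below 10%. The zero-event statement therefore needs the 95% level attached.
- Confidence level, retention: if true retention were 80%, the chance of 23 or more retained is 24 × 0.8^23 × 0.2 + 0.8^24 = 0.0283 + 0.0047 = 3.3%. That is above 2.5% but below 5%. So 23/24 fails to exclude 80% two-sided but would do so one-sided at 95%. The statement that only 24/24 does so is a two-sided one.

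**The case against.** Descriptive analysis is normal in a pilot, and the plan claims no test for these outcomes. Its wording says that the descriptive statistics include frequencies and percentages, which does not forbid intervals. The counts will be reported, so any reader can compute limits. The cut-offs can already be read as benchmarks for the enrolled sample. Participant protection does not rest on the 10% figure: Data and Safety Monitoring provides for review of adverse events, and Quality control and assurance for serious-event reporting.

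Most of this is fair, and it limits the point to how the primary results are reported and worded. It does not remove it. An interval is itself descriptive, none is planned, and the hypothesis is worded as a conclusion about the intervention. That readers could compute limits does not correct a conclusion already drawn from the point estimate.

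Three stronger readings are tempting and not supported:

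- **That these outcomes decide whether a larger trial goes ahead.** The background says that feasibility is to be examined before a formal trial, but no go/no-go rule appears anywhere. Objectives ties the planning of a larger trial to the tertiary outcomes.
- **That intervals would stop a poor program passing or a good one failing by chance.** At 24 participants a true event rate of 15% meets the safety cut-off 28% of the time, and true retention of 75% meets the retention cut-off 25% of the time. True retention of 85% misses it 29% of the time. These figures follow from the cut-offs and the sample size, and reporting intervals changes none of them.
- **That the data could never support either claim.** For retention, 24/24 does exclude values below 80%.

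**Conclusion.** The point holds as one about the precision and wording of the primary conclusions. At the 95% level, results that meet the cut-offs are compatible with retention as low as 62.6% and an adverse-event rate as high as 27.0%. No result in 24 people has an upper limit below 10% for adverse events, since even 0/24 gives 14.2% two-sided or 11.7% one-sided. Only 24/24 retained has a two-sided interval wholly above 80%.

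This rests on three assumptions. The 95% level is ours. The figures for 24 pool the two arms, and the documents do not say whether the cut-offs apply to both arms together or to the exercise arm; in one arm of 12 the limits are wider (0/12: up to 26.5%; 10/12: 51.6% to 97.9%). They also assume that recruitment reaches 24, which is itself one of the feasibility outcomes.

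A reader might infer that the trial is too small or that the program is likely to be unsafe. Neither follows. With no events, an upper limit below 10% would need 29 participants (one-sided) or 36 (two-sided), but the pilot is not obliged to exclude 10%. It is obliged only not to claim that it has.

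**What to change.** 1. **Statistics, primary outcomes.** Add that the retention and adverse-event proportions will each be reported with an exact (Clopper-Pearson) two-sided 95% confidence interval, overall and by arm.
2. **Objectives.** Keep the 80% and 10% cut-offs as percentages, but call them observed benchmarks. Percentages still apply if fewer than 24 are randomized, whereas fixed counts would not. Limit the conclusion to a form such as: *benchmark met (or not met); at the 95% level the data exclude retention below X% and an adverse-event proportion above Y%.*
3. **Statistics, sample size.** Keep the pilot rationale and add the precision it gives. For example, with 24 participants, 20 retained gives 62.6% to 95.3% and no adverse events gives an upper limit of 14.2%; with 12 in one arm, 10 retained gives 51.6% to 97.9% and no events gives an upper limit of 26.5%.

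The cost is a few sentences and one table column. Sample size, procedures and data collection do not change. The real price is that the stated conclusions on feasibility and safety will be less favourable.

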- Inclusion/exclusion criteria align with the samples that were engaged in our community-engaged foundational studies and numerous clinical trials in persons with MS and other wheelchair users such as spinal cord injury.
- Participants will be recruited using clinic visits at UTHealth Houston and Harris Health MS clinics and flyers in the local community. Specifically, [name] will facilitate contact with potential participants in the UTHealth Houston and Harris Health clinics.

Study Procedures

- Interested participants will contact the Study Coordinator for a telephone screening, which includes a comprehensive description of the study followed by screening for inclusion criteria. Participants deemed eligible for the study will then be sent a consent form to review and sign using through REDCap. When the Study Coordinator receives the signed consent form, participants will be mailed a pre-test/baseline assessment packet. The pre-test assessment packet will include Actigraph GT3X+ accelerometer and instructions to wear the accelerometer on the non-dominant wrist for 7 days as well as an order for blood sample collection at a Quest Diagnostics/LabCorp location that is convenient for them. Participants will complete a battery of questionnaires online using REDCap. When the Study Coordinator receives the accelerometer and notification that a blood sample has been collected, participants will be randomized into the exercise training intervention condition or attention/contact control condition using the REDCap randomization module. Following randomization, participants will be mailed their condition-specific program materials as well as instructions for downloading Zoom. All participants will receive behavioral coaching, which is founded in Social Cognitive Theory (SCT) behavior change principles. Each participant will meet one-on-one with the same behavioral coach, the PI, weekly for the first 8 weeks of the program, and biweekly for the last 8 weeks (total of 12 meetings). Meetings will be recorded for auditing and training purposes as outlined in the consent form. The research team created 12 SCT-based, condition-specific newsletters that serve as the curriculum underpinning each program. Post-test assessment of tertiary outcomes following the 16-week intervention will mirror baseline

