accommodation period). Participants are then assigned to one of three trajectories of progression over the remaining 14-week period to reach a final goal of at least two, 30-minute aerobic workouts per week. Fifteen resistance training exercises were developed that include body weight movements and use of study-provided resistance bands or wrist weights for targeting upper body, core muscle groups, and lower body that are adaptable for manual or power wheelchair users. During the proposed program, participants will choose the resistance training exercises those that best suit their functional capabilities and goals. The resistance training prescription begins with 1 set of 10 repetitions of 5 exercises performed 2 days a week. Similar to the aerobic exercise prescription, three trajectories of progression for the resistance training will be used (i.e., sets, repetitions, and exercises) over the remaining 14 weeks to reach a final goal of at least 2 sets of 15 repetitions of 10 exercises. The participant manual includes instructions on precautions and safety for exercise that will be reviewed with all participants during the first coaching call. Coaches will check-in regularly with each participant to assess safety and report any adverse events to IRB.

- Wellness Intervention: The attention/contact wellness control condition will mirror the exercise training intervention condition, but focuses on implementing health behaviors other than physical activity (e.g., diet and emotional wellbeing) over 16 weeks. This program is an adapted version of the WellIMS program from [name] III clinical trial (NCT03490240) that [name] delivered and coached during an initial postdoctoral fellowship. The program is based on SCT principles of behavior change and integrates wellness resources from the NMSS. The research team has created 12 Newsletters split into six different topics, with each topic addressed in two newsletters. The topics include Stress Management, Emotional Regulation, Diet, Sleep, Balance and Fall Risk, and Fatigue. All coaching chats and newsletters will occur with the same frequency as in the exercise training intervention condition. Participants will be provided with a participant manual, logbook, and calendar. Participants will work with their behavioral coach on goal setting specific to wellness behaviors.

Data and Safety Monitoring

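### The planned mixed ANOVA leaves baseline out as a covariate: a valid analysis of the tertiary outcomes, but usually less precise than baseline adjustment, which could cost only about 5-6% of variance

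*Combined protocol and SAP*

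**What the plan says.** Statistics states that the outcomes of the third hypothesis "will be examined using 2 time by 2 group mixed factor ANOVA with estimation of Cohen's d values for effect sizes". It adds a benchmark: "change in scientific outcomes will be further examined and compared with the ≥ 0.5 SD will be considered meaningful change". Baseline enters only as the first level of the time factor. Neither this section nor any other names a baseline covariate.

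Objectives gives the purpose of these comparisons: "for determining effect size and sample size estimates in powering a larger clinical trial". Study Design classes them as tertiary, after feasibility (primary) and acceptability (secondary).

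Study Procedures shows that baseline values will exist. For the devices and blood tests, they must be in before allocation: "When the Study Coordinator receives the accelerometer and notification that a blood sample has been collected, participants will be randomized". The questionnaires are described before that step but are not part of the stated trigger. The follow-up uses the same measures: "Post-test assessment of tertiary outcomes following the 16-week intervention will mirror baseline".

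**The concern.** In a two-arm trial with one baseline and one follow-up value, the time-by-group F statistic is the square of the t statistic on change scores. Subtracting the whole baseline value amounts to fixing the slope of post-test on baseline at 1. ANCOVA estimates that slope from the data. When the true slope is well below 1, change scores carry baseline noise into the arm difference.

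The stake is limited but specific. The tertiary analysis is there to supply a planning estimate, and with 12 people per arm its confidence interval is wide. A more efficient estimator from data already collected would narrow it at almost no cost. The arms would be compared without bias either way.

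**Working it through.** **The plan's own figure.** The sample is 2 x 12 = 24 randomized. No alpha, power, effect size or SD is stated, so there is no power calculation to reproduce.

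**Inputs from the documents.** There are 24 randomized participants, 12 per arm, and two assessments. The retention target is "retaining ≥80% of those participants through the full 16-week study period"; 0.80 x 24 = 19.2, so 20 completers meets it.

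**Assumed inputs.** Rho is the baseline/post-test correlation and k is the post-test SD divided by the baseline SD. The documents give neither, so both are shown as ranges. Baseline is taken as normal with SD 1, and the relation as linear with the same slope in both arms.

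**Formulas**, with n per arm and N = 2n:

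- Change-score variance = (1 + k² - 2·rho·k) x 2/n
- ANCOVA variance = k²(1 - rho²) x 2/n x [1 + 1/(N - 4)]

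The bracket is the price of estimating the slope: 1.05 at N = 24 and 1.0625 at N = 20.

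**Example**, k = 1.0, rho = 0.5, N = 24: change score 1 + 1 - 1 = 1; ANCOVA 0.75 x 1.05 = 0.7875. The variance is 21% lower.

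**Example**, k = 1.5, rho = 0.7: change score 1 + 2.25 - 2.1 = 1.15; ANCOVA 2.25 x 0.51 x 1.05 = 1.205. The ratio is 1.048, so ANCOVA is 5% worse.

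**Variance ratio, ANCOVA / change score, N = 24** (below 1 favors ANCOVA):

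| k | rho 0.3 | 0.5 | 0.7 | 0.8 | 0.9 |
|---|---|---|---|---|---|
| 0.9 | 0.609 | 0.701 | 0.789 | 0.828 | 0.851 |
| 1.0 | 0.683 | 0.788 | 0.892 | 0.945 | 0.997 |
| 1.1 | 0.746 | 0.858 | 0.967 | 1.016 | 1.050 |
| 1.25 | 0.824 | 0.938 | 1.030 | 1.050 | 0.997 |
| 1.5 | 0.915 | 1.013 | 1.048 | 1.001 | 0.816 |

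With 20 completers, the k = 1.0 row becomes 0.691, 0.797, 0.903, 0.956, 1.009, and the k = 1.25 row becomes 0.834, 0.949, 1.042, 1.062, 1.009.

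**Where ANCOVA is worse at N = 24:** rho above 0.905 (k = 1.0), 0.765-0.966 (k = 1.1) and 0.626-0.898 (k = 1.25). At k = 0.9 it is better at every rho.

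**Upper bound on the loss.** (1 + k² - 2·rho·k) - k²(1 - rho²) = (1 - rho·k)², which is never negative. So the ratio cannot exceed 1 + 1/(N - 4), whatever rho and k are. That is a 5.0% loss at N = 24 and 6.25% at N = 20. Counting the lost degree of freedom as well, the 95% CI is at most 2.8% or 3.5% wider.

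**CI half-width in baseline SDs, N = 24, change score to ANCOVA:**

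- rho 0.5: 0.85 to 0.75 (k = 1.0); 0.97 to 0.94 (k = 1.25)
- rho 0.7: 0.66 to 0.62 (k = 1.0); 0.76 to 0.78 (k = 1.25)

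**Simulation check**, 12 per arm: savings of 31.8% and 21.4% (k = 1.0, rho 0.3 and 0.5), 17.4% and 6.1% (k = 1.25, same rho), and a 4.9% loss at k = 1.25, rho 0.8. These agree with the formulas. If only the exercise arm's post-test SD rises to 1.25, the ratios across the five rho values are 0.766, 0.877, 0.981, 1.032 and 1.051.

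**The case against.** The strongest reply is that nothing is wrong. The planned test is valid, it already uses baseline through the change, and it matches hypotheses worded as greater improvement. That stands: a reader might infer that the mixed ANOVA is an error or is biased, and the documents do not support that. But ANCOVA estimates the same arm difference under randomization, so fit to the question is no reason to prefer change scores.

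A second reply is that the size of the gain is unknown. This also stands. A reader might take a gain of 6-32% (rho 0.3-0.5, ratio 1.0-1.25) as the expected benefit. No figure in the documents favors those values over a higher rho or a larger ratio, where the gain disappears or turns slightly negative. Nor is 5% the worst case at the retention target; with 20 completers it is 6.25%.

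Third, exercise behavior might be thought to have a larger SD at post-test. Entry requires "being non-active defined as not engaging in regular physical activity", and in the exercise arm "Participants are then assigned to one of three trajectories of progression". The first could compress the baseline SD. The second is weak evidence of later spread, because all three trajectories lead to the same minimum goal. A larger post-test SD would in any case weaken the argument for ANCOVA over much of the range, so neither passage supports the point.

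Fourth, the randomization trigger covers blood and accelerometry, not questionnaires. That is a fair limit, and the fix allows for it.

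Finally, the plan does not say which SD divides Cohen's d. That is a reporting gap, separate from the choice of covariate, and adds no weight here.

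**Conclusion.** The point holds as one of efficiency. For the tertiary outcomes, baseline adjustment is usually more precise than the planned change comparison, and its possible loss is small and bounded. Across the assumed grid the expected variance runs from about 39% lower to 5% higher at 24 participants. The favorable end needs a low rho or a post-test SD no larger than baseline. Outcomes that are very stable over 16 weeks, with SD ratio near 1, would gain almost nothing.

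The bound of 5% (24 completers) or 6.25% (20) does not depend on rho or k, but it does assume the linear, normal-baseline model above. The case for ANCOVA as the default rests on that asymmetry, because the plan itself says there is no prior information from which to choose.

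A reader might infer that the trial's main conclusions are at risk. They are not: feasibility and acceptability are summarized descriptively and are unaffected. With 24 people, the efficacy estimates stay imprecise under either analysis.

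**What to change.** In Statistics, pre-specify for each tertiary outcome an ANCOVA of the post-test value on randomized arm and baseline value. Report the adjusted mean difference with its 95% CI, and name it in advance as the estimate for planning the larger trial. State that questionnaire baselines must be completed before randomization to serve as the covariate. The mixed ANOVA and the 0.5 SD comparison can remain as supplements.

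The cost is two or three sentences and no new data. Each outcome loses one residual degree of freedom (21 instead of 22 with 24 participants), with the small possible loss of precision shown above.

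As a separate reporting addition, give the baseline SD, the post-test SD, their correlation and the SD used for Cohen's d for each outcome. The next sample-size calculation can use them whichever analysis it adopts.

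### For the tertiary outcomes, an analysis labelled intent-to-treat uses only participants with both assessments, and the plan does not say that post-tests are sought from those who stop the program

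*Combined protocol and SAP*

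**What the plan says.** All references are to the combined protocol and SAP.

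- **Statistics, principle:** "The analysis will use the intent-to-treat principle where patients will be" "analyzed in their randomization assignment". This is the whole definition. It fixes the arm in which a person is counted and says nothing about people without outcome data.
- **Statistics, method for Hypothesis 3:** the scientific outcomes "will be examined using 2 time by 2 group mixed factor ANOVA", with Cohen's d as the effect size.
- **Study Procedures:** "Post-test assessment of tertiary outcomes following the 16-week intervention will mirror baseline" assessments. There is one post-test. No sentence makes it conditional on finishing the program, and none says it is sought from someone who stops.
- **Objectives, feasibility:** the goals are "reaching recruitment goals (n=24; 12 per group) within a one-year period" and "retaining ≥80% of those participants through the full 16-week study period".
- **Objectives, third hypothesis:** changes in the scientific outcomes are to supply effect size and sample size estimates for a larger trial.

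The document names no imputation method, likelihood-based model, analysis set or missing-data sensitivity analysis. Primary and secondary outcomes are summarized descriptively and are not affected by this point.

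**The concern.** A mixed-factor ANOVA with two time points needs both values from each participant. Anyone without a post-test leaves the comparison, although the baseline has been collected. The result is a complete-case analysis under an intent-to-treat label.

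Loss may also differ by outcome. Blood draw, accelerometer and questionnaires are separate tasks, and participants may skip questionnaire items.

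If the people lost differ from those who stay, in baseline level or in response, the effect size does not describe the 24 who were randomized. That effect size is the figure to be carried into the next trial's sample size.

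**Working it through.** **1. Loss compatible with the plan.** The plan randomizes 12 × 2 = 24. The retention floor is 0.80 × 24 = 19.2, so at least 20 must be retained: 20/24 = 83% passes and 19/24 = 79% fails. Up to 4 of 24 (16.7%) can be lost with the goal met. Up to 28 are to be consented ("therefore we aim to consent up to 28 participants"), but that allowance covers losses before randomization.

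**2. What the ANOVA uses.** With two time points, the time-by-group F equals the squared two-sample t on (post − baseline). On a simulated set of 24 with 4 post-tests removed, both came to 2.725 on 20 − 2 = 18 error degrees of freedom, against 22 with all 24.

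**3. Direction and size of bias.** The documents give no effect size, correlation or dropout pattern, so all of these are assumed: 12 per arm, true effect 0.50 SD, baseline–post correlation 0.7, and 2 or 4 post-tests missing. The table shows mean estimates over 10,000 simulated trials. The adjusted column regresses post-test on arm and baseline. With two time points, this is the maximum-likelihood arm effect from a mixed model with a common baseline mean.

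| Who is lost (2 / 4) | ANOVA | Baseline-adjusted |
|---|---|---|
| Random | 0.50 / 0.50 | 0.50 / 0.50 |
| Lowest baseline, exercise arm | 0.42 / 0.35 | 0.50 / 0.50 |
| Worst response, exercise arm | 0.71 / 0.90 | 0.69 / 0.85 |
| Worst response, both arms | 0.39 / 0.33 | 0.40 / 0.35 |

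The bias runs either way. Adjustment removes it when loss depends on baseline and barely moves it when loss depends on response.

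**4. Precision with no loss** (same assumptions). The standard error for change scores is √(2(1 − 0.7) × 2/12) = √0.100 = 0.32. For the baseline-adjusted estimate it is √((1 − 0.7²) × 2/12) = √0.085 = 0.29, or about 0.30 once the slope is estimated. A mixed model with separate baseline means per arm would not give this gain, because with complete data it reproduces the ANOVA contrast.

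**5. A one-sided illustration** (assumed). Four exercise participants stop with no gain and give no post-test, the other 8 gain 0.6 SD, and controls do not change. The ANOVA gives 0.6, while the effect over all randomized is (8 × 0.6 + 4 × 0)/12 = 0.4, so the overstatement is 0.6/0.4 − 1 = 50%. With 2 lost per arm, the effect is (10 × 0.6 + 2 × 0)/12 = 0.5 and the overstatement is 20%. If stopping is unrelated to baseline, the mixed model also returns 0.60 in both cases. Only the missing post-tests would correct it.

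**6. Consequence for the larger trial** (two-sided 0.05 and 80% power, both assumed). Per arm, n = 2(1.960 + 0.842)²/d² = 15.70/d². An analyzed d of 0.5 gives 63. If k exercise participants are lost and gained nothing, the all-randomized d is 0.5 × (12 − k)/12:

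| k | d | n per arm needed | Power at 63 per arm |
|---|---|---|---|
| 1 | 0.46 | 75 | 73% |
| 2 | 0.42 | 91 | 65% |
| 3 | 0.38 | 112 | 56% |
| 4 | 0.33 | 142 | 46% |

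In the other direction, a true 0.50 estimated as 0.35 gives 15.70/0.35² = 128.2, so 129 per arm where 63 would do.

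**The case against.** **The effect sizes need not describe completers only.** A reader might infer that they do, but the documents do not support it. Study Procedures gives the post-test a time, not an adherence condition. It also compensates all participants for each assessment and invites all to the interview. Someone who stops exercising but returns the packet stays in the ANOVA. The affected group is participants lacking a post-test, and on post-tests after stopping the plan is silent rather than prohibitive. This part of the objection stands.

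**The intent-to-treat definition is met.** Analysis by randomized arm satisfies the plan's own wording. That is correct as far as it goes. The fault is that nothing covers missing outcomes, so the label suggests more than the method delivers.

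**The plan does not forecast 20% loss.** The 80% figure is a hypothesized feasibility threshold, and retention is not defined as post-test completion. It shows what loss is tolerated, not what is expected.

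**Bias in favor of exercise is not established.** A reader might infer it from the thought that those who tolerate exercise poorly leave. The document gives no dropout reasons or rates by arm, and the simulation produces bias in both directions.

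**Changing the model does not cure the 50% illustration.** This stands: the mixed model returns the same 0.60. Its case rests on baseline-related loss and on precision.

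**With 12 per arm, sampling error is large anyway.** The standard error of about 0.32 SD exceeds several of the biases in the table. That limits how much weight the pilot effect size can bear, but it is no reason to leave an avoidable bias in place.

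**Conclusion.** The concern holds for the tertiary outcomes only. The named ANOVA uses participants with both assessments, nothing in the plan offsets that, and the plan does not commit to obtaining post-tests from those who stop. Up to 4 of 24 can be missing with the retention goal met.

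The size of any bias rests on assumed values and on who is lost. It is nil under random loss, and the loss issue does not arise if all 24 return for every outcome. The direction cannot be stated in advance. The point deserves a change because these effect sizes are meant to power the next trial, but it does not threaten the feasibility or acceptability results.

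**What to change.** 1. **Follow-up.** State in Study Procedures that stopping coaching or exercise is not withdrawal from the study, and that week-16 assessments (accelerometer, lab order, REDCap questionnaires) are sought from every randomized participant who has not withdrawn consent. This is the main protection against response-related loss, and it is feasible because the assessments are mailed, online or at a local laboratory.
2. **Analysis.** In Statistics, replace the ANOVA with a likelihood-based linear mixed model with a common baseline mean (time, arm-by-time) on all observed values. State its missing-at-random assumption and report the numbers analyzed per arm and outcome. Keep the ANOVA as a sensitivity analysis labelled complete-case. Say plainly that the model corrects baseline-related loss and improves precision but does not correct response-related loss. Its benefit comes from conditioning on baseline: a participant with a baseline alone still adds no direct information on the arm difference.

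**Cost.** The change needs a few sentences in the protocol and SAP, plus assessments and payments for the few who stop early. At the retention floor the payments are at most 4 × $75 = $300, plus laboratory and mailing costs, which the document does not give. Including these participants may lower the apparent effect.
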